19.3. Safety Outcomes

The safety outcomes for this study are hospitalizations and deaths (SAEs).

SAEs will be summarized by type and by treatment group in terms of frequency of the event, number of subjects having the event, timing relative to randomization, and relatedness to the study treatment (related, possibly related, not related). Despite the relatively large sample in this trial, we anticipate incidence of possibly treatment related hospitalizations and deaths to be relatively rare so do not propose any formal statistical tests of the SAE data.

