Because the patients who participate in the RESOLVE study will be older and have co-morbid health conditions, it is expected that subjects will experience inpatient hospitalizations, which are unrelated to study participation, during the course of the study. In addition, it is expected that deaths, which are also unrelated to study participation, might occur among study enrollees based on prior studies. Specifically, in the study PI's recently completed pragmatic trial, PPACT, which provided an intensive in-person behavioral intervention and enrolled 850 patients with chronic pain, there were 12 deaths during the study, all unrelated to study participation, and 287 hospitalizations (116 for intervention participants and 171 for usual care).

SAEs will be systematically assessed every 6 months for active study participants based on electronic health records (EHR) data.

- Each clinical site will query active participants' electronic health records data every 6 months (in alignment with the DSMB meeting schedule) to identify any deaths or hospitalizations throughout the interval of active participant enrollment in the trial.
- An independent physician within each health care system/clinical site will conduct a chart review for each death and hospitalization to assess its potential relatedness to study procedures and interventions.
- The summary of SAEs and findings of these reviews will be submitted to the DCC.

In addition to the semi-annual EHR queries, SAEs may be identified by participant self-report. If this occurs, the event will be documented and reviewed by the independent physician as part of the semi-annual review described above.

12.1.3 *Definition of Adverse Events of Special Interest (AESI)*

This protocol will not collect solicited adverse events of special interest (AESI). There is no clinical or empirical basis for hypothesizing that either of the active interventions would increase risk of AESIs. In addition, the unequal contact with study staff among participants in the three study arms inherently results in differential opportunities for ascertainment of "events." Therefore, between-group comparison of adverse events reported to or discovered by study staff would be biased and hence not meaningfully interpretable or actionable.

12.1.4 *Severity of Adverse Events*

For an AE, the following guidelines will be used to describe severity:

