5.0. Sample Size Determination for the Primary and Secondary Effectiveness Analyses

For our primary study outcome, clinically meaningful improvement (MCID; 30% reduction in overall BPI-SF score) in pain severity at 3 months, we calculated sample size requirements for a two-sided comparison of independent proportions with 90% power using Fisher's Least Significant difference method to account for three-way comparisons (specifically conduct Omnibus Wald Test for any difference between three groups and then conduct pairwise comparisons given an overall difference is statistically significant at the 0.05 alpha level). Sample size calculations assumed a usual care outcome rate of 15% who achieve the MCID of 30% reduction in pain severity from baseline to 3 months. The 15% usual care rate was chosen because we observed this rate among participants in the usual care arm of our recently completed PPACT trial¹⁷ and it is similar to rates observed by others in the usual care arm of similar trials.¹⁸ We calculated the necessary sample size of 1,863 (621 per arm) to detect a difference of 7.5% between a given intervention group relative to usual care in the proportion of individuals who attain a clinically meaningful change (30% reduction from baseline) in pain severity. We estimate a retention rate of 80%. Thus, to achieve this final sample size, we will randomize 2,331 individuals, 777 per intervention arm. A 7.5% detectable difference corresponds to 22.5% (relative change of 150%) of individuals in an intervention arm attaining a clinically meaningful change in pain severity.

We also estimated power for secondary analyses related to aim 1b (subgroup analyses). We calculated sample size requirements for these secondary analyses using the same assumptions described above (i.e., a two-sided comparison of independent proportions using Fisher's Least Significant difference approach to account for three-way comparisons, with sample size calculations assuming an improvement rate of 15% in the usual care arm). We ranged our subgroup sample size between 20% and 40% of the original 1,863 sample size since this should cover the range of the subgroup sample sizes of interest.

Power for Subgroup Analyses Ranging the Size of the Subgroup

Assumptions		80% Power to Detect:		
Subgroup Sample Size	Usual Care (UC)	Intervention (Int)	Detectable Difference	Relative Change
N (% of 1,863)	% UC	% Int	% Int - %UC	% Int / %UC
372 (20%)	15.0%	31.0%	16.0%	206.7%

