8.0. Randomization

After completion of the baseline data collection, study participants will be individually randomized in equal ratio to one of the three study arms.

Randomization will be stratified on:

Variable	Source
Sex	Sex from electronic health record (Male vs. Female or Other)
Pain severity score	Score on BPI-SF from baseline survey (< 7 vs. ≥ 7)
Clinical site	KPWA, KPNW, KPGA, Essentia
Rural/medically underserved residency	Residency geocode for Census Tract from electronic health record

Within each stratum, to contain concealment and balance randomization over time, a random permuted block design will be used with random variable block sizes of 3, 6, or 9 to ensure approximately equal accrual into the three study arms.

The TIN JHU/Tufts Lead biostatistician will develop the randomization scheme and the TIN Utah DCC will implement the scheme using the appropriate statistical software. The scheme to be implemented will be integrated into the study centralized tracking system.

Randomization will be conducted by KPWHRI research staff within the study centralized tracking system after consent and baseline assessment completion.

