19.1. Adverse Events

An adverse event (AE) is any untoward or unfavorable medical occurrence in a human subject, including abnormal signs, symptoms, or diseases, temporarily associated with the subject's participation in the research, whether or not considered related to the subject's participation in the research. Because the RESOLVE study population includes patients with chronic pain, who have fluctuating physical and emotional symptoms as part of the natural course of their condition, such symptoms will not be systematically solicited as part of the trial.

Specifically, AEs will be identified if participants proactively contact the study team at any time to self-report AEs or self-report during a regular study contact; or by intervention or study staff who are interacting with participants regularly throughout the intervention. Since AEs will not be solicited uniformly from all study participants, collection of these events will be biased by study arm (i.e., telephone CBT-CP participants will have greater interaction with study staff by phone and more opportunity to self-report these symptoms and events). AEs will be documented and tracked; a report of the frequency of AEs by site will be reviewed by the PI quarterly and provided to the DSMB on a semi-annual schedule.

Although we considered the possibility of examining other events of special interest particularly those of interest for the HEAL initiative overall (e.g., suicidality), we decided this was not advisable both because there is no clinical or empirical basis for hypothesizing that either of the active interventions would increase risk of events of special interest and because the unequal contact with study staff among participants in the different study arms inherently results in differential opportunities for ascertainment of "events." In this circumstance, between-group comparison of adverse events reported to or discovered by study staff would be biased and hence not meaningfully interpretable or actionable.

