19.4. Descriptive Analyses

The safety analyses will be performed using descriptive statistics to quantify hospitalizations and deaths (SAEs) by usual care control arm and separately by each intervention arm. As the study is not powered to test for non-inferiority of the safety events by exposure to the interventions compared to the usual care control, no statistical tests will be performed on group differences in the SAE safety.

19.5. Summary of AEs and SAEs by MedDRA Code and Grouped by Organ System

Because this trial focuses exclusively on behavioral interventions MedDRA codes covering pharmaceuticals, biologics, vaccines, and drug-device combination products are not applicable.

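### The SAP summarizes hospitalizations by arm but plans no between-arm estimate or interval, although all-cause hospitalization may be common enough to give a useful one

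*SAP*

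**What the plan says.** SAP 19.3 makes hospitalizations and deaths the safety outcomes. They are to be summarized by treatment group: event frequency, number of participants affected, timing and relatedness. The SAP anticipates the incidence of "possibly treatment related hospitalizations and deaths to be relatively rare so do not propose any formal statistical tests of the SAE data". SAP 19.4 repeats that the analysis is descriptive and gives a second reason for having no tests: "As the study is not powered to test for non-inferiority of the safety events by exposure to the interventions". Neither section plans a rate ratio, a risk difference or a confidence interval between arms.

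SAP 19.2 has each site query active participants' EHR every six months for deaths and hospitalizations. Self-report is a supplementary route. Hospitalizations scheduled before enrolment are not SAEs.

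Protocol 12.1.2 says hospitalizations are expected and gives a precedent from an earlier pragmatic trial in chronic pain, which "enrolled 850 patients with chronic pain, there were 12 deaths during the study, all unrelated to study participation, and 287 hospitalizations". The documents give no expected number of hospitalizations for this trial.

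**The concern.** Both stated reasons argue against a hypothesis test. The first is about events judged possibly related to treatment. All-cause hospitalization needs no such judgement, and the protocol's own precedent suggests it is not rare. The second is a reason not to claim non-inferiority. It says nothing against showing how precisely a difference was measured.

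Readers will compare by-arm counts whether or not the SAP does so. Without an interval they cannot tell a chance imbalance from a real one. The trial would also be unable to say what size of increase in hospitalization its data exclude, although it may hold several hundred events.

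**Working it through.** **Inputs.** Earlier trial: 850 patients, 287 hospitalizations, 12 deaths (Protocol 12.1.2). This trial: "we will randomize 2,331 individuals, 777 per intervention arm" (SAP 5.0), "individually randomized in equal ratio to one of the three study arms" (SAP 8.0), enrolled for 12 months (SAP 1.0).

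**Randomized number.** SAP 5.0 needs 621 evaluable per arm at 80% retention: 621 / 0.80 = 776.25, rounded up to 777; 3 × 777 = 2,331. The plan's figure reproduces. There is no stated hospitalization figure to reproduce.

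**Expected hospitalizations, if the earlier rate applied.** 287 / 850 = 0.338 per patient. 0.3376 × 2,331 = 787 in all; 0.3376 × 777 = 262 per arm. At half the rate, about 394 in all and 131 per arm.

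**Precision of one active arm against usual care.** With E events in each arm and overdispersion φ (φ = 1 is Poisson; larger values allow for repeat admissions), SE(log rate ratio) = √(2φ / E). The 95% interval is the estimate multiplied and divided by exp(1.96 × SE).

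- Full rate, φ = 1: √(2 / 262) = 0.087; factor 1.19.
- Full rate, φ = 2: √(4 / 262) = 0.123; factor 1.27.
- Half rate, φ = 2: √(4 / 131) = 0.175; factor 1.41.

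| Share of earlier rate | Total events | Per arm | Factor, φ = 1 | Factor, φ = 2 | Factor, φ = 3 |
|---|---|---|---|---|---|
| 100% | 787 | 262 | 1.19 | 1.27 | 1.35 |
| 75% | 590 | 197 | 1.22 | 1.32 | 1.41 |
| 50% | 394 | 131 | 1.27 | 1.41 | 1.52 |

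If the observed rate ratio were 1, the upper limit would therefore be 1.19 in the best case shown and 1.52 in the worst.

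**Deaths.** 12 / 850 × 777 = 11 per arm. √(2 / 11) = 0.43, a factor of about 2.3. Counts are enough.

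**Ascertainment.** The bias argument in SAP 19.1, that "the unequal contact with study staff among participants in the different study arms inherently results in differential opportunities for ascertainment", is made about events reported to or discovered by staff. The six-monthly EHR query in SAP 19.2 does not depend on staff contact. Two qualifications remain. Self-reported hospitalizations could differ by arm. Only active participants are queried, so different withdrawal by arm would change the time at risk.

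**The case against.** The strongest reply is that the SAP is consistent and has not hidden anything. It declines tests and reports events and affected participants by arm. The DSMB receives safety analyses twice a year, and the trial is described as minimal risk. All of that stands. What remains is an omission, which a short addition would mend.

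A second reply is that SAP 18.0 already plans a modelled comparison between randomized groups, with in-patient hospital as a category. That comparison is of costs, for the Kaiser sites with Essentia conditional. It gives no event-rate ratio and does not fill the gap.

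A third is that the 787 is extrapolated. This is right. The earlier trial's follow-up and arm sizes are not given, and titles in the protocol's reference list describe its patients as long-term opioid users. Here pre-scheduled admissions are not counted, and people with pain-related surgery planned in the next 12 months are excluded. The half-rate row is there for this reason, and it still leaves about 394 events.

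Four stronger readings are tempting, and the documents do not support them.

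- A reader might infer that the plan forbids any between-arm safety estimate. It rules out tests and is silent on estimates.
- A reader might set the 787 against the word rare. That word is used of possibly treatment-related events, so there is no contradiction. Nor is unequal staff contact offered as a reason about EHR-queried SAEs.
- A reader might take the earlier trial's "287 hospitalizations (116 for intervention participants and 171 for usual care" as evidence of a reduction: 116 / 171 = 0.68 if the arms were equal. The arm sizes are not given, and the reference list calls it a cluster randomized trial. With SE √(1/116 + 1/171) = 0.120 and |ln 0.68| = 0.388, the 95% interval reaches 1 once the variance is inflated by (0.388 / (1.96 × 0.120))², about 2.7. Overdispersion of 2 with a cluster design effect of about 1.35 would do that.
- A reader might ask for emergency visits coded for overdose or self-harm as well. SAP 19.1 gives a separate reason for not examining events of special interest, namely no clinical or empirical basis for expecting an increase. The SAE query covers only deaths and hospitalizations.

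**Conclusion.** The point holds as an omission. The reasons in SAP 19.3 and 19.4 justify having no formal test, but they do not justify having no interval for all-cause hospitalization. On the assumption that the earlier trial's rate applies in full or by half, about 787 or 394 hospitalizations would be expected. A rate ratio against usual care would be known to within a factor of about 1.19 (full rate, Poisson) to 1.41 (half rate, overdispersion 2), or 1.52 if overdispersion reached 3. That is precise enough to say something useful about hospitalization risk. For deaths the descriptive plan is adequate.

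A separate inconsistency needs reconciling. Protocol 12.1.2 has an independent physician chart-review each death and hospitalization for relatedness. SAP 19.2 says hospitalizations are not routinely chart-reviewed. This bears on how the relatedness summary in SAP 19.3 is filled in.

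**What to change.** In SAP 19.3 and 19.4, keep the statement that no formal tests will be done and add:

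- For each active arm against usual care, the rate ratio for all-cause, EHR-identified hospitalization per person-time, with a robust 95% confidence interval that allows for repeat admissions, labelled as estimation only.
- Hospitalizations known only from self-report, listed separately by arm.
- Person-time and withdrawals by arm, because only active participants are queried.
- The same estimate for the Kaiser sites alone as a check, because SAP 18.0 affirms full capture of utilization only there.
- Deaths as counts by arm, as now planned.

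Reconcile Protocol 12.1.2 and SAP 19.2 on chart review of hospitalizations.

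The cost is a few lines of SAP text and one regression on data already extracted for safety monitoring. The downside is a few intervals not adjusted for multiplicity, which the estimation-only label should make plain.

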19.4. Descriptive Analyses

The safety analyses will be performed using descriptive statistics to quantify hospitalizations and deaths (SAEs) by usual care control arm and separately by each intervention arm. As the study is not powered to test for non-inferiority of the safety events by exposure to the interventions compared to the usual care control, no statistical tests will be performed on group differences in the SAE safety.

19.5. Summary of AEs and SAEs by MedDRA Code and Grouped by Organ System

Because this trial focuses exclusively on behavioral interventions MedDRA codes covering pharmaceuticals, biologics, vaccines, and drug-device combination products are not applicable.

19.6. Safety Monitoring and Recruitment Suspension Rules

The DCC will monitor the safety data and will notify the DSMB chair per the protocol specified in the DSMP. The DSMB chair will provide recommendations regarding the temporary suspension of enrollment and/or administration of study procedures or study interventions and an ad-hoc DSMB meeting will be convened.

20.0. Interim Analyses

There are no planned interim analyses of primary or secondary outcome data before the study is completed. However, if in context of evaluating the safety outcomes the DSMB requests interim effectiveness estimates they will be provided. No formal futility or effectiveness interim analyses will be conducted.

